8.6 Correlation between organ SUV and irAEs

Organ SUV (higher than background uptake vs. equal to or lower than background uptake) will be correlated to irAE (yes or no) using the Chi Square test.

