The ability of PET to quantitatively image the distribution of radiolabeled drugs within the body makes this technique a valuable tool for drug development and application. Immuno-PET allows to learn about the ideal drug dosing for optimal tumor targeting (e.g., saturation of receptors), the uptake in critical normal organs to anticipate toxicity, and the variation in pharmacokinetics and tumor targeting. Drug imaging is able to provide this information in an efficient and safe way. Pretreatment imaging with the drug of interest can be used for patient selection because it can show target expression and drug accumulation in tumor lesions and normal tissues noninvasively, quantitatively, and over time. This information might be particularly relevant for heterogeneous target expression or when targeted drugs are combined with other treatment modalities like parallel pathway inhibition, to find routes of synergism. In this way, immuno-PET can be used for better understanding of *in vivo* biology (“immunohistochemistry *in vivo*”) (50).

To enable visualization of a targeted drug with a PET camera, the drug should be labeled with a positron emitter in an inert way, i.e., that neither binding nor pharmacokinetic characteristics of the drug become altered. Moreover, the physical half-life of the positron emitter should be compatible with the residence time of the targeted drug in the body, which is typically several days for slow kinetic intact mAbs. Universal procedures exist for radiolabeling of intact mAbs with the long-lived positron emitter Zirconium-89 (⁸⁹Zr, t_{1/2} = 78.4 h) (51).

During the past years, several preclinical and clinical ⁸⁹Zr-immuno-PET studies have been performed with intact mAbs, for example with mAbs against cMET, EGFR, VEGF and HER2 (52-55).

The first clinical ⁸⁹Zr-immuno-PET study ever was reported in 2006 by Börjesson et al. (56). This feasibility study with 20 head and neck cancer patients showed that ⁸⁹Zr-cmAb, directed

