5.2 Sample size

Twenty patients will be included in this study. A formal power analysis to calculate a sample size is not feasible due to the explorative nature of this trial. The sample size of 10 patients in each arm is based on two previous analyses that we performed. In a cohort of 9 head and neck cancer patients we were able to find significant differences in the expression of activation markers between different dendritic cell subsets (data on file). In a cohort of 9

melanoma patients we were able to find significant differences in the expression of activation markers between dendritic cell subsets of patients with a Breslow thickness more or less than 1.5 mm (60).

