5.3.2.4 Blood sample analysis

Blood samples (7 mL) will be withdrawn at 10 min post-injection, 72 hours and 144 hours post-injection of ^{89}Zr -pembrolizumab to determine ^{89}Zr -kinetics based on measurements of radioactivity.

5.3.2.5 ^{89}Zr -pembrolizumab PET procedure

All PET scans will be performed on a Philips Ingenuity TF PET/CT scanner.

All patients will undergo two whole body PET scans at $t = 72$ and $t = 144$ hours post-injection. The PET scans will be preceded by a 30 mAs low-dose CT, used for attenuation correction and anatomical localization of the PET-signal. Following CT, a total body PET scan will be acquired. PET scans consist of 10-12 bed positions, depending on the length of the patient, of 5 minutes each. Total acquisition time per scan, including low dose CT will be around 60 minutes.

PET data will be normalized and corrected for randoms, tissue attenuation, decay, scatter and dead time. PET-CT data will be reconstructed with TF-OSEM, resulting in a transaxial spatial resolution of ~ 7 mm in the centre of the field of view. Regions of interest (ROIs) will be defined using the CT images which are co-registered to the PET-CT data. ROIs around the organs which accumulate ^{89}Zr (e.g. liver, lung and other metastatic lesions) will be drawn manually directly on the PET images. All tissue concentrations will be related to the blood concentration (venous samples). The radioactivity concentrations in all regions for all imaging time points will be recorded digitally in a spread sheet.

Quantitative accuracy of ^{89}Zr -PET scans was previously confirmed in our center using phantom studies and comparisons between PET-derived and biopsy tumor radioactivity concentrations (64, 65).

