6.0 TRIAL FLOW CHART

6.1 Study Flow Chart

Trial period	Screening Phase	Imaging	Induction treatment phase	Surgery	Follow-up
Scheduling Window (Days)	-30 to -1	-14 to 0	From day 1 to day 56 (2 weeks after 2 nd pembrolizumab cycle)	From day 56 to day 70	From surgery to 6 months thereafter
Administrative Procedures					
Informed Consent	X				
Eligibility Criteria	X				
Demographics and Medical History	X				
Prior and Concomitant Medication Review	X				
PET Imaging					
⁸⁹ Zr-pembrolizumab		X ^a			
Clinical Procedures/Assessments					
Review Adverse Events	X		X ^b		
Full Physical Examination	X				
Directed Physical Examination	X		X ^b		X ^c
Vital Signs and Weight	X		X ^b		
ECOG Performance Status	X		X ^b		
12-lead ECG	X				
¹⁸ F-FDG PET-CT		X		X	
Laboratory Procedures/Assessments					
Pregnancy Test	X				
Complete Blood Count (CBC)	X	X ⁱ	X ^b		
Comprehensive Serum Chemistry Panel	X		X ^b		
Urinalysis	X				
T3, FT4 and TSH	X		X ^d		
Treatment					
SBRT			X		
Pembrolizumab			X ^a		
Surgery				X	
Efficacy Measurements					
Tumor Imaging (CT thorax +/- abdomen and MRI brain)		X	X ^e		X ^f
Tumor Tissue and Blood analysis					
Core tumor biopsy	X				
EBUS FACS		X	X ^g		
Surgical resection specimen				X	
Immunophenotyping		X ^h	X ^h	X ^h	X ^h

X^a: only for patients randomized to the SBRT + pembrolizumab arm; X^b: every cycle; every 6 weeks; X^c: if indicated; X^d: after 2nd pembrolizumab cycle; X^e: within 2 weeks of surgery; X^f: following resection every 3 months for the first 2 years and every 6 months for the 3 years thereafter; X^g:; X^g:between week 2 and 3 after SBRT; . X^h: see section 7.1.2.10 for timepoints; Xⁱ: 72 and 144 hours post-injection for patients undergoing ¹⁸F-FGD-PET-CT

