8.3 Analysis of PET data

SUV_{max} , SUV_{mean} and SUV_{peak} will be measured in all tumor lesions, enlarged lymph nodes and liver, kidneys, lungs, spleen and left ventricle of the heart.

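### Section 8.6 replaces the measured organ SUV with a split at an undefined background; in tracer-accumulating organs this may leave all or nearly all of about 10 scanned patients in one category, and a different 2x2 test would not help

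*Combined protocol and SAP*

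**What the plan says.** Section 8.6 codes each organ as above background, or equal to or below it: "Organ SUV (higher than background uptake vs. equal to or lower than background uptake) will be correlated to irAE (yes or no", with the chi-square test. It does not say what background is, which SUV metric or which scan is used, whether each organ gets its own table, or whether the irAE must be in the imaged organ. It states no significance level.

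The input is a measured quantity. Section 8.3 says SUVmax, SUVmean and SUVpeak "will be measured in all tumor lesions, enlarged lymph nodes and liver, kidneys, lungs, spleen and left ventricle of the heart", and section 8.5 treats SUV as continuous. Section 5.3.2.5 schedules scans at 72 and 144 hours, relates tissue concentrations to venous blood, and speaks of "ROIs around the organs which accumulate" the tracer, naming liver and lung among its examples.

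The flow chart in section 6.1 marks the tracer scan as "only for patients randomized to the SBRT + pembrolizumab arm". Section 5.2 says: "The sample size of 10 patients in each arm is based on two previous analyses that we performed". About 10 patients can therefore enter the table.

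**The concern.** A cut at background asks whether an organ takes up tracer at all. Relating uptake to irAEs requires knowing which patients take up more than others. If most patients fall on the same side of the cut, the 2x2 table has an empty or nearly empty row. It then says little about the association, whatever the truth is. Moving from chi-square to Fisher's exact test does not repair this, because the information is lost at the cut and not in the test. The continuous values that could show a link are already being collected.

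What is at stake is one exploratory analysis. The risk is that an uncomputable or very lopsided table is read as evidence of no association.

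**Working it through.** The plan gives no power, effect size or rate for this analysis, so there is no figure of its own to reproduce.

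**Inputs from the documents.** n = 10 scanned patients (sections 5.2 and 6.1); binary exposure and chi-square (8.6).

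**Assumptions.** Two-sided 0.05; k = 3, 4 or 5 irAE patients; log SUV normal with SD 1 and higher by d = 1.5 or 2.0 SD in irAE patients; share p of irAE-free patients above background of 30%, 50%, 80% or 95%. The documents give no any-grade irAE rate. Section 4.1.7 gives only 9.5% for drug-related grade 3-4 events and 1.8% for pneumonitis, from a trial in NSCLC.

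**Step 1: what a lopsided table can show.**
- 10/0 split: one row is empty, chi-square is undefined, and Fisher's p is 1 by construction.
- 9/1 split: the most extreme table has probability 1/10, so the smallest Fisher p is 0.10. Uncorrected chi-square can reach 10 × (9 × 1)² / (9 × 1 × 1 × 9) = 10, p = 0.0016. With few irAEs this happens only when the single low-uptake patient is the one with the irAE, the reverse of the expected direction.
- 8/2 split: the smallest Fisher p is 1/C(10,2) = 1/45 = 0.022. With two irAEs, this requires both to be in the two low-uptake patients.

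**Step 2: how often the split is that lopsided.** With a common probability p of being above background, P(10/0) = p^10 and P(at least 9 above) = p^10 + 10p^9(1 − p).

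| p | all 10 above | at least 9 above |
|---|---|---|
| 50% | 0.001 | 0.011 |
| 70% | 0.028 | 0.149 |
| 80% | 0.107 | 0.376 |
| 90% | 0.349 | 0.736 |
| 95% | 0.599 | 0.914 |

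**Step 3: power with a real link.** If a share p of irAE-free patients is above the cut, the share among irAE patients is q = Φ(z_p + d), where z_p is the p-quantile of the standard normal. All ten are above with probability p^(10−k) × q^k. For p = 0.80, k = 3, d = 1.5: q = Φ(0.842 + 1.5) = 0.990, giving 0.8^7 × 0.990³ = 0.210 × 0.971 = 0.204. For k = 5, d = 2.0: q = 0.998, giving 0.8^5 × 0.998^5 = 0.328 × 0.989 = 0.324. Power is the sum of Bin(a; k, q) × Bin(b; 10 − k, p) over the tables with test p ≤ 0.05, where a and b are the numbers above background with and without an irAE. Ranges over k = 3-5 and d = 1.5-2.0:

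| irAE-free above background | row empty | chi-square (uncorrected) | Fisher |
|---|---|---|---|
| 30% | under 1% | 41-63% | 19-41% |
| 50% | 1-3% | 19-45% | 5-17% |
| 80% | 20-32% | 0.5-6% | under 1% |
| 95% | 70-77% | about 0.1% or less | about 0 |

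An exact Mann-Whitney test on continuous SUV, simulated under the same assumptions, has power of about 37-69% whatever the cut.

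**Step 4: limits of the continuous analysis.** The smallest two-sided exact Mann-Whitney p is 2/C(10,k): 2/10 = 0.20 for one irAE patient, 2/45 = 0.044 for two, and 2/120 = 0.017 for three. With one irAE patient it cannot reach 0.05. With a shift of 0.8 SD, power is only about 12-16% for two to five irAE patients (100,000 simulated trials each: 12.3%, 12.5%, 15.5%, 14.1%). Under another assumed model (odds ratio 4 per SD, irAE probability 20-50% at mean SUV) it is about 19-27%, against 0.5% or less for the split with Fisher when 90% or more of patients are above background.

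**The case against.** The strongest reply is that the size of the loss depends on a share the documents never give. A reader might infer that nearly every patient will be above background in liver and lung, so that the split cannot separate patients. Section 5.3.2.5 does not support that. It says where regions of interest are drawn, mixes organs with metastatic lesions in its examples, and gives no proportion. If background means venous blood, which 8.6 does not say, lungs or left ventricle could fall on either side in different patients. This stands, and the conclusion has to be conditional. It also stands that an even split is not the best case for 8.6: at 30% above background, uncorrected chi-square is close to Mann-Whitney. It is a liberal test at this size, however, and Fisher stays lower.

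Three further points stand.
- The phrase "the uptake in critical normal organs to anticipate toxicity" in section 4.2.5 describes immuno-PET in general. It might be read as an aim of this trial, but the PET objective in section 3.2 covers tumor and lymph nodes only, and no listed objective links organ uptake to irAEs.
- Table 3 might be read as a list of irAE organs to set against the organs scanned. It is a dose-modification table for drug-related events with a row for all other toxicity, and the left ventricle may be measured as blood pool.
- Section 8.6 does not say that organs are analysed separately. Pooled patient-organ pairs could fill both rows, but those observations would not be independent.

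The reply does not give a reason to discard the measured SUV. Under the assumed shifts of 1.5-2.0 SD, the continuous analysis beat Fisher on the split at every share examined.

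**Conclusion.** The concern holds in conditional form. Section 8.6 gives up a continuous measurement for a cut at an undefined background in about 10 patients, and the cut may leave one row empty or with a single patient in organs expected to accumulate tracer. Where that happens, no change of 2x2 test rescues the analysis. With 3-5 irAE patients and a 1.5-2.0 SD shift, the loss is large if 80% or more of irAE-free patients are above background, and small for uncorrected chi-square if about 30% are. Shift, irAE count and share above background are all assumed.

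A reader might also infer that a real link would be reported as absent. An empty row would be visibly uninformative, so the documents do not support that as a certainty; the milder risk is that a 9/1 table is over-read. Keeping SUV continuous makes the analysis better but not confirmatory. Severity is low: the analysis is exploratory, is tied to no listed objective, and section 5.2 disclaims formal power.

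**What to change.** Replace the split in section 8.6 with text such as:

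*For each organ in 8.3, one prespecified SUV metric at one prespecified scan time (72 or 144 h), or its tissue-to-blood ratio, is kept continuous and compared between patients with and without an irAE by exact Mann-Whitney test, with the AUC and its 95% CI. Results are descriptive, without multiplicity control across organs. For liver, lungs and kidneys, any irAE of that organ is listed against the patient's SUV rank for that organ.*

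Fixing the metric and scan time matters because five organs × three metrics × two scans would otherwise allow 30 comparisons. The cost is SAP wording only, with no new scans or data. The downside is that the analysis stays descriptive at this sample size. Organ-matched events are likely to be very few, so that part can only be a listing.

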4.2.3 Translational research

Because the mode of action of combined SBRT and anti-PD-1 therapy is unknown, it is essential to perform translational research to identify the mechanisms of action and toxicity before effect size studies can be initiated with recurrence free and overall survival as outcome parameters.

Serial invasive and noninvasive measurements of immune biomarkers will be performed for the primary tumor, lymph nodes and peripheral blood. A study schedule is provided in section 2.2. In short, the translational research will include:

- Biological imaging of tumor PD-1 expression in patients randomized to combination radiotherapy and pembrolizumab treatment with ⁸⁹Zr-pembrolizumab immuno-PET prior to treatment initiation. Biological imaging of PD-1 expression allows non-invasive *in-vivo* monitoring of PD-1 binding. To visualize PD-1 engagement by pembrolizumab we use a novel technique called immuno-PET in which positron emission tomography (PET) is combined with a radiolabeled monoclonal antibody. Imaging with radiolabelled pembrolizumab (⁸⁹Zr-pembrolizumab) allows for non-invasive quantification of its direct target, the PD-1 receptor on tumor infiltrating lymphocytes. Because the technique is non-invasive and whole body, it allows to evaluate tumor heterogeneity (volumetric analysis of tumor PD-1 expression).
- Immunohistochemical examination of immune effector subsets in a tumor core biopsy specimen at baseline. The following markers will be evaluated for expression: PD-1, PD-L1, CD4, CD8 and FoxP3, combined with Ki67 double staining.
- Multicolor flowcytometric assessment of immune effector subset rates and activation state in peripheral blood and TDLNs by means of endoscopic ultrasound guided fine needle aspiration (EBUS-FNA) at baseline and after SBRT +/- pembrolizumab treatment. The following subsets/populations will be included in this analysis: (memory/effector) CD4+ and CD8+ T cells, Tregs, granulocytic and monocytic MDSCs, conventional and plasmacytoid DCs, and macrophages.
- Three-dimensional tumor and lymph node histological examination of immune effector subsets in the resection specimen after SBRT +/- pembrolizumab treatment. This enables to
 - Explore intratumor heterogeneity of immune effector subsets after SBRT +/- pembrolizumab treatment, possibly associated with therapeutic resistance.

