4.2.4 Rationale for Endpoints

This an exploratory study that aims to evaluate the safety of the trimodality approach and characterize the immunological mechanisms of action of combination radiotherapy and immunotherapy. Therefore the primary endpoints of this study are the tolerability and toxicity of combined SBRT +/- pembrolizumab treatment and surgery and to analyze the immunological antitumor response. The endpoints will be assessed by clinical signs of

radiation pneumonitis and examination of tumor core biopsies and resection material, FACS analysis on EBUS-FNA of TDLNs and peripheral blood to detect immunomodulation.

Secondary endpoints are the correlations of *in-vivo* PD-1 expression, quantified by immune-PET, with tissue and blood based immune-parameters.

The levels of PD-1 and PD-L1 expression are variable over time (see section 4.1.8) and expression has been found to be heterogeneous between and within tumor lesions of the same patient. The biomarker PD-L1 IHC is currently being validated in multiple clinical studies to stratify patients based on the intensity and percentage of positive staining. This trial is a unique opportunity to study the 3-dimensional uptake of ⁸⁹Zr-pembrolizumab in the tumor and correlate the imaging result with the 3D immunohistochemistry results of the surgical tumor specimen.

Although pneumonitis will be assessed as a symptom, an exploratory objective is to evaluate radiation induced changes to healthy lung tissue after SBRT +/- pembrolizumab treatment in the resected lung lobe.

The number of patients (n=10 in each arm) is too low to correlate study parameters to clinical outcome in terms of progression-free or overall survival.

4.2.5 ⁸⁹Zr-pembrolizumab imaging

To identify patients that will benefit the most from treatment with mAbs like pembrolizumab, better knowledge of the *in vivo* behavior of the drug is warranted. For this, positron emission tomography (PET) imaging with radiolabeled mAbs (immuno-PET) is an attractive option.

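### Section 8.6 applies a chi-square test to 2x2 tables of about 10 patients, where its p-value can be far too small; an exact test should be named (low severity)

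*Combined protocol and SAP*

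**What the plan says.** Section 8.6 makes organ uptake binary, "Organ SUV (higher than background uptake vs. equal to or lower than background uptake", and says that it "will be correlated to irAE (yes or no) using the Chi Square test". It names no exact alternative, continuity correction or rule for small cells. It gives no significance level, and it does not say whether the patient or the organ is the unit.

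The number of patients follows from other sections. The flow chart in 6.1 marks the zirconium PET as "only for patients randomized to the SBRT + pembrolizumab arm", and 4.2.3 agrees: "Biological imaging of tumor PD-1 expression in patients randomized to combination radiotherapy and pembrolizumab treatment". Section 5.2 sets the size of that arm: "The sample size of 10 patients in each arm is based on two previous analyses that we performed". Section 8.3 lists where uptake is measured, which besides tumor lesions covers "enlarged lymph nodes and liver, kidneys, lungs, spleen and left ventricle of the heart", so five organs. Section 8.6 does not say which of them are tested.

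**The concern.** The chi-square p-value is a large-sample approximation. With about 10 patients and possibly only a few irAEs, the expected counts are small and the approximation can fail. A single coincidence in one patient could then be reported as a strong association between organ uptake and toxicity.

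Section 4.2.5 presents uptake in normal organs as a way to anticipate toxicity, so such a result might be taken up. The analysis could be repeated over up to five organs, and section 8 has no multiplicity rule.

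**Working it through.** The plan gives no figure for this analysis, so there is nothing of its own to reproduce.

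**Inputs.** n = 10 scanned patients (5.2, 6.1, 4.2.3). Both variables are binary (8.6). A two-sided 0.05 level is assumed, because 8.6 states none. The documents give no irAE rate and no rate of raised uptake, so both are assumed and varied from 10% to 50%. The nearest figures are in 4.1.7, from an earlier trial: 9.5% drug-related grade 3-4 events and 1.8% pneumonitis. Neither is an irAE rate.

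**Expected counts.** With r irAEs and m high-uptake patients, the expected count in the joint cell is r x m / n. The smallest of the four expected counts is greatest when both variables split evenly: 10 x 0.5 x 0.5 = 2.5. No margin pair therefore reaches 5 in every cell. With 1-2 irAEs and 1-3 high-uptake patients the smallest expected count lies between 1 x 1 / 10 = 0.1 and 2 x 3 / 10 = 0.6. Replacement under 5.11 could raise n slightly; at n = 12 the ceiling is 12 x 0.25 = 3.

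**One table in full.** One irAE, one high-uptake patient, the same person: a = 1, b = 0, c = 0, d = 9.

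- Chi-square = n(ad - bc)² / (product of the four margins) = 10 x 9² / (1 x 9 x 1 x 9) = 10, so p = 0.0016 on 1 degree of freedom.
- Given these margins, the two patients coincide by chance 1 time in 10, so Fisher p = 0.10. The ratio to the unrounded chi-square p is 64.
- Boschloo gives 0.077 and Barnard 0.039. Fisher with mid-p gives 0.5 x 0.10 = 0.05.

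**Other tables, n = 10, all irAEs among the high-uptake patients.**

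| irAEs | High uptake | Chi-square p | Fisher p |
|---|---|---|---|
| 1 | 1 | 0.0016 | 0.100 |
| 1 | 2 | 0.035 | 0.200 |
| 2 | 3 | 0.016 | 0.067 |
| 3 | 5 | 0.038 | 0.167 |
| 4 | 6 | 0.035 | 0.076 |

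**All tables.** There are 9 x 9 = 81 pairs of non-empty margins and 246 tables. Chi-square (uncorrected) gives p < 0.05 in 62 of them, and in 32 of those 62 Fisher p is 0.05 or more. In all 62 the chi-square p is smaller than Fisher's, by a factor of 2.2 to 64.

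**False-positive rate given the margins, nominal 5%.** For margins up to 5:

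- 0%: 1/3, 1/4, 1/5, 2/4, 2/5
- 0.8%: 3/3, 5/5
- 2.2%: 2/2
- 3.3%: 3/4
- 4.8%: 4/5
- 6.7%: 2/3
- 7.6%: 4/4
- 10%: 1/1
- 16.7%: 3/5
- 20%: 1/2

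Over all 81 pairs, 28 exceed 5% and 53 do not.

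**Average over random margins.** With both rates assumed at 10-50% and no association, the chi-square test rejects in 1.6-5.4% of trials. That average counts tables with an empty margin, which cannot be tested, as non-rejections. At 10% for both variables the chance of an empty margin is 1 - (1 - 0.9¹⁰)² = 1 - 0.651² = 0.58. Among testable tables the rejection rate is then 0.0475 / 0.424 = 11.2%. At 10%/20% it is 8.6% and at 20%/20% it is 6.8%. With both rates at 30% or more it is about 4-5%.

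**Continuity correction.** Yates' correction does not repair this. In the 1/1 table it gives 0.160 against Fisher's 0.100, and in the 1/2 table 0.429 against 0.200.

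**The case against.** The strongest reply is that neither margin is fixed by design, so the fair measure is the error rate over random margins, and that is close to nominal: 1.6-5.4% for assumed rates of 10-50%, and 5.8% at most on a wider grid. This stands. A reader might infer that the chi-square test greatly inflates false positives overall; the calculation does not support that, apart from the 7-11% among testable tables when both rates are an assumed 10-20%. What the average does not settle is the individual p-value. A reader of the results sees one table, and 66-98% of the null rejections behind that average are not significant by Fisher.

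A second reply is that Fisher gives the widest contrast. This is also fair. In the 1/1 table Barnard's 0.039 is itself below 0.05, and in the 3/5 table Boschloo gives about 0.06-0.07, not 0.167. Fisher is also very conservative here: its size over random margins is only 0.1-1.8%. Even so, the smallest of these exact p-values in the 1/1 table is about 25 times the chi-square value (0.039 / 0.0016, rounded).

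A reader might also take the single-coincidence table to be the one most likely to occur. The documents give no rates from which to say so. At an assumed 10% for both variables its probability is (10 x 0.1 x 0.9⁹)² x 0.1 = 0.387² x 0.1 = 1.5%, and a table that cannot be tested is far commoner.

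Finally, 5.3.2.5 says "All patients will undergo two whole body PET scans", which might suggest n = 20. Read with 6.1 and 4.2.3 it means all patients given the tracer. Even at n = 20 only a 10/10 split of both variables reaches an expected count of 5 in every cell (20 x 0.5 x 0.5 = 5).

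**Conclusion.** The point holds, at low severity. At n = 10 the smallest expected count is at most 2.5 whatever the event rates. In particular tables the chi-square test in 8.6 can report evidence far stronger than any of the exact tests examined. The size of the error is specific to the table: 0% to 20% given the margins, with 28 of 81 margin pairs above 5%, and near nominal on average. The p-values and margin-specific rates rest on n = 10 and, where rejection is counted, on a 5% level. The averages rest also on assumed rates and on independence of uptake and irAE.

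It would be wrong to infer that a trial conclusion is at risk. Relating organ uptake to irAEs is not among the primary, secondary or explorative objectives in 3.1-3.3. The safety criterion in 8.1 uses pneumonitis alone, 5.2 describes the trial as explorative without a power basis, and 10.3.2 says imaging does not guide treatment. The consequence is a misleading nominal finding.

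**What to change.** In 8.6, replace the chi-square test with an exact test, preferably Boschloo's or Fisher's with mid-p. State that the patient is the unit and that there is one table per organ, and list the organs. Pooling five organs over 10 patients into 50 observations would treat repeated measurements on a patient as independent. If Boschloo's test is chosen, state in advance which variable defines the groups. Report each table's counts with an exact confidence interval for the difference or odds ratio, and label the results descriptive.

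The cost is a few sentences in the plan, with no change to data collection, sample size or procedures. Plain Fisher would almost never reject at n = 10, and mid-p eases this by giving up Fisher's guaranteed error bound. No choice of test makes 10 patients informative, so the counts and intervals should carry the report.
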